Since hypothesis testing is not recommended for pilot studies, no formal hypothesis testing on the efficacy of the intervention will be performed in this pilot trial for the primary and secondary outcomes. However, estimates of the difference or the relative ratio between arms, with 95% confidence intervals, will be obtained that will provide information on the direction and possible range of the intervention effect which may be used as a basis to support a larger RCT. We will compare the ACT group to the TAU group on retention in care and undetectable VL 6 months after hospital discharge with descriptive statistics calculated for these primary outcomes. Assuming a composite outcome (retention in care and VL improvement) of between 30% and 65%, a sample size of N=35/group will allow us to estimate the outcome rate for each group to within 15 to 17 percentage points (95% CI). Estimates of the difference between treatment arms will also be assessed for exploratory outcomes, including mental health, stigma, and coping. Likewise, descriptive statistics will be computed for the demographic, clinical, and baseline variables to describe the characteristics of the pilot study sample population. These analyses

will also help validate our methods and data gathering techniques. These descriptive analyses will also be performed for the sub-populations that we anticipate will have more difficulty relinking to outpatient HIV care (e.g., substance abuse).

Study Timeline

Timeline	Yr 1				Yr 2		
Recruit 70 pts (10/m): follow for 6m	X	X	X	X	X		
Review EMR, analyze data, finalize protocols, publish					X	X	

We anticipate enrolling 8-10 persons per month and should complete enrollment in < 9 months. We will need 6 months to follow the last participants. We will also need time for data analysis and final protocol revisions. The pilot study will be completed within 18 months.

Recruitment, Consent, and Enrollment

Screening

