voluntary nature of the study. The research coordinator will be prepared to answer any questions. Potential participants will be told that their decision to participate in the study or not will not affect the clinical care he/she receives. If the patient is still interested, they will be asked to provide consent. In addition, the patient will sign a HIPPA authorization form.

Randomization

This study will randomize at the participant level. Randomization will occur following enrollment in the study. The study statistician will generate the randomization sequence to ensure adequate distribution of the two interventions over the study period. The randomization sequence will be maintained by the statistician in a password protected file.

Blinding

Neither participants nor study personnel are blinded in this study.

Study Intervention

A therapist trained in Acceptance and Commitment Therapy (ACT) will provide the ACT based intervention individually at the bedside as 4 individual, 30-40 minute sessions. If study participants complete the THRIVE intervention sessions, he or she will have opportunities to 1) reflect on personal values and personal barriers that could prevent them from living out those values on a day-to-day basis, 2) receive education specific to HIV and managing HIV, 3) HIV stigma, and 4) coping skills. Subjects will be asked to document a goal that will be reviewed at the booster session.

A research team member will work with each participant prior to discharge to schedule the booster session and follow-up assessments. Prior to the participant's first scheduled outpatient follow-up visit with TSHC, the therapist will call participants to check on them and conduct an individualized phone booster session. This phone call will last 20-40 minutes. Participants will receive a reminder call/message approximately 1 day before the session.

Therapist Training

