- Review material and skills learned throughout the intervention.
- Consider values from first session and what action can be taken in the service of them now (and as discharged from the hospital).
- Teach SMART goals (specific, meaningful, achievable, realistic, time-limited) to assist patient in making a concrete plan to incorporate value-driven behavior and decrease avoidant coping in their life.

PHONE BOOSTER

- Discuss any difficulties patient has had connecting with care. Use ACT skills and matrix framework to conceptualize any barriers.
- Review ACT Matrix and key points from intervention.

Post-Intervention Evaluations

Evaluation Overview

Participants will receive the THRIVE intervention or treatment as usual. Treatment is assigned by random allocation. Participants will receive the intervention during their hospital stay. For evaluation purposes, enrolled patients will provide baseline demographic, clinical, and behavioral data. The information will be self-report or gathered through medical record review. Follow-up assessments will occur 3- and 6-months post-discharge. Assessments will include coping skills, stigma, depression, anxiety, stress, substance use, and client satisfaction. Medical record data will include HIV laboratory testing results and medications as well as data on kept and missed HIV primary care appointments. The medical record review will include retrospective data and data for the year after enrollment. The baseline survey contains 85 items and should take 30 minutes, while the 3- and 6-month follow-up surveys contain 70 and 60 items, respectively.

To avoid bias, the 3- and 6-month assessments will take place in the field, e.g., at the patient's residence, at a Harris Health facility other than the HIV clinic, or at other mutually agreed upon and safe places. They will not be allowed to occur at TSHC. Any self-reported use of health resources external to Harris Health System will be verified by medical record review.

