All patients have a VL done as standard of care in the hospital. We will obtain 6-month VL by study phlebotomy in the field (not at the clinic, to avoid biasing participants to return to the clinic to obtain the compensation for the assessment visit) and review the EMR for additional VLs to minimize missing data. About 10 mL of blood will be drawn per participant at the 6-month evaluation. All VL assays will be conducted by the BTH laboratory, a fully certified clinical laboratory that performs all HIV-related

laboratory studies for TSHC and BTH.

Participants will provide detailed contact information and permissions at enrollment (e.g., what numbers are OK for text messages and voice messages, whether contacts are aware of the participant's HIV status, etc.). All contact with the participants' associates and family will not reveal that the participant has HIV or is involved in research. Contact information will be updated at all follow-up interviews.

Participants will also complete a brief phone call with the research coordinator to verify and update contact information at 2, 8 and 18 weeks after hospital discharge. These calls are to promote retention in assessment visits. Participants will be given a card with the study's telephone number (no information traceable to HIV will be included). Phone interviews will be used for follow-up assessments as a last resort.

The 2-week call will also include the CSQ and satisfaction self-report assessments for participants in the THRIVE arm.

[3-month Follow-up Self-Report](#)

At 3 months, the survey will include: Coping; IARSS; DASS-21; AUDIT-C; ASSIST.

[6-month Follow-up Self-Report](#)

At 6 months, the survey will include: Coping; IARSS; DASS-21; AUDIT-C; ASSIST; Chart Review; and HIV VL.

[6-month Chart Review](#)

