When a data collection session is completed, the research coordination will review electronic forms for completeness and validity. The research coordinator will resolve all queries and will enter an override for all values that have been confirmed as being accurate. Reports will also be run periodically to confirm or correct questionable values. All changes will be tracked through the REDCap audit trail. Assessments completed on paper will be entered into REDCap by the research coordinator.

The data entered into the REDCap database is stored on servers at Baylor College of Medicine and is backed-up on a regular basis.

Strategies for minimizing missing data

1. Reviewing all surveys for completeness before finalizing.
2. Reviewing all electronic medical records for internal and external records.
3. Requesting medical records for participants who report use of external facilities.

Protocol Deviations

Protocol deviations will be recorded as they are known to happen on a hard-copy form and then entered in the study's Tracking Database to compile an electronic log for reporting purposes. Quarterly hard-copy-to-electronic-copy audits of Protocol Deviation forms and audits of consent forms will be performed.

Monitoring

Data will be routinely monitored at the time of data collection. REDCap will be used to collect data and the researchers will be prompted at the end of each session to check missing entries. Regular team meetings will be held where researchers can report ongoing data collection concerns to ensure proper adherence to the protocols and high-quality data collection. Audio files will be stored on a secure BCM server. Only the participants' ID will be used to identify the participants. Coordinators will ensure the data is de-identified.

Summary of Measures at Each Evaluation

Type of Measure	Measures	Baseline Visit	THRIVE: In-hospital sessions (4hrs.)	THRIVE: Phone booster session (.5 hrs.)	Post-discharge	2 wk.	3 mo.	6 mo.
Characterize Sample. Possible Covariates	Demographic/ Medical Information	X						
	Coping Skills	X			X	X		
Primary Outcomes	Retention in HIV Care	X					X	
	HIV VL	X					X	
Exploratory: Stigma & Mental Health	Stigma	X			X	X		
	Depression, Anxiety, and Stress	X			X	X		
	Substance Use	X			X	X		
Treatment Satisfaction	Client Satisfaction		X					

Data Collection Instruments

Demographics/Medical Information

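### Arm differences on the exploratory coping, stigma and mental health scales could be estimated more precisely by adjusting for the baseline scores already collected (optional)

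*Combined protocol and SAP*

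**What the plan says.** The Sample Size section rules out formal efficacy testing for the primary and secondary outcomes and relies on estimates with 95% confidence intervals. For the exploratory scales it states: "Estimates of the difference between treatment arms will also be assessed for exploratory outcomes, including mental health, stigma, and coping". The next sentence gives the one stated use of baseline variables: "descriptive statistics will be computed for the demographic, clinical, and baseline variables to describe the characteristics of the pilot study sample population". The Data Analysis Plan (Analysis Methods) covers feasibility and acceptability summaries and their benchmarks, and has no method for these scales.

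The scales are measured repeatedly. The Evaluation Overview says that "enrolled patients will provide baseline demographic, clinical, and behavioral data", and the Summary of Measures table marks coping, stigma and depression/anxiety/stress at the baseline visit. The follow-up sections then list: "At 3 months, the survey will include: Coping; IARSS; DASS-21; AUDIT-C; ASSIST" and "At 6 months, the survey will include: Coping; IARSS; DASS-21; AUDIT-C; ASSIST; Chart Review; and HIV VL".

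The only mention of covariates is a label in the Summary of Measures table, "Characterize Sample. Possible Covariates", which stands beside demographics and coping. Stigma and mental health stand beside a different label, "Exploratory: Stigma & Mental Health". No analysis is attached to either.

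On timing, the Randomization section says "Randomization will occur following enrollment in the study", and the Blinding section says that neither participants nor staff are blinded. The documents do not say whether the baseline survey is completed before the arm is known.

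**The concern.** The pilot rests on interval estimates, and with 70 participants those intervals are wide. When the same instrument is given before and after, part of the spread in follow-up scores is predictable from the baseline score. Removing that part narrows the interval for the arm difference and needs no new data. The plan does not say that it will do this. What is at stake is precision on exploratory outcomes and nothing more.

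**Working it through.** **The plan's own precision figure.** The Sample Size section claims 15 to 17 percentage points for each arm's composite rate, with 35 per group and rates of 30% to 65%. The Wald half-width 1.96 × √(p(1−p)/35) gives 15.2 points at p = 0.30, 16.6 at p = 0.50 and 15.8 at p = 0.65. The figure reproduces. It concerns the binary composite and does not bear on the exploratory scales, for which the plan states no precision.

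**Inputs for the exploratory scales.**
- n = 35 per arm and a 95% interval: Sample Size section.
- Outcome SD set to 1, so results are in SD units.
- r, the correlation between the baseline and follow-up score: not in the documents; assumed from 0 to 0.7.
- n = 28 per arm as a sensitivity case: 0.80 × 35 = 28. The 80% is borrowed from the benchmark for appointment and viral load data, so applying it to the surveys is an assumption.

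**Formulas, one visit at a time.**
- Unadjusted: t(0.975, 2n−2) × √(2/n)
- ANCOVA: t(0.975, 2n−3) × √[(2/n)(1−r²)(1 + 1/(2n−4))]

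The last factor is the average cost of estimating the baseline slope.

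**n = 35.** Unadjusted: 1.9955 × √(2/35) = 1.9955 × 0.2390 = 0.477 SD. Adjusted at r = 0.5: 1.9960 × √(0.05714 × 0.75 × 1.01515) = 1.9960 × 0.2086 = 0.416 SD. The same formula gives:

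| r | Adjusted half-width (SD) | Change from 0.477 |
|---|---|---|
| 0 | 0.481 | about 1% wider |
| 0.2 | 0.471 | 1% narrower |
| 0.3 | 0.459 | 4% narrower |
| 0.4 | 0.441 | 8% narrower |
| 0.5 | 0.416 | 13% narrower |
| 0.6 | 0.385 | 19% narrower |
| 0.7 | 0.343 | 28% narrower |

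Setting the two half-widths equal gives a break-even r of 0.12.

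**n = 28.** Unadjusted 0.536 SD; adjusted 0.516, 0.469 and 0.386 SD at r = 0.3, 0.5 and 0.7 (again 4%, 13% and 28% narrower). Break-even r is 0.14.

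**Equivalent sample size.** Ignoring the small degree-of-freedom cost, adjustment is worth 35/(1−r²) per arm unadjusted: about 38 at r = 0.3, 47 at r = 0.5 and 69 at r = 0.7.

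**Why ANCOVA and not change from baseline.** The change score multiplies the variance by 2(1−r). With the normal quantile and n = 35, its half-width is 1.96 × √((2/35) × 2(1−r)): 0.55 SD at r = 0.3, 0.47 at r = 0.5 and 0.36 at r = 0.7. The unadjusted comparison on the same basis is 1.96 × √(2/35) = 0.47. Change scores therefore lose precision below r = 0.5, whereas ANCOVA loses at most about 1%.

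**The case against.** The strongest reply is that nothing here is an error. The unadjusted difference is valid, the outcomes are exploratory, and no benchmark in the Data Analysis Plan depends on these intervals. That stands, and it is why the point is only optional.

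The gain also rests on an r that the documents do not give, and several features suggest it may be low. DASS-21 asks about the past week only, entry requires endorsing an avoidance coping item (which may restrict the baseline range of that subscale), and baseline is taken during a hospital stay. At r = 0.2 to 0.3 the half-width falls by only 0.006 to 0.018 SD, which would hardly change how a pilot interval is read. This also stands. The answer is only that the possible loss is about 1% and the possible gain is larger.

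The proposal would produce 14 models (seven scores at two visits) in 70 people. They replace 14 simple differences that the plan already implies, and no tests are planned, so the burden is small.

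A reader might infer three stronger things, none of which the documents support:
- *That the plan excludes adjustment.* It is silent. Its wording is compatible with ANCOVA, and the table does speak of possible covariates. Because that table is damaged in extraction, its row grouping is weak evidence either way.
- *That visits and scores are undefined.* The Evaluation Overview and the follow-up sections fix 3 and 6 months. The instrument sections define the IARSS as a 0–6 count and the DASS-21 as three subscales. Only the choice among the three coping domains is open, and that is a separate matter of outcome definition.
- *That pre-specifying ANCOVA is needed to prevent a choice made after seeing the data.* A pre-stated unadjusted difference would do that equally well.

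**Conclusion.** The point holds as an optional gain in precision for the exploratory scales. The plan states no use of baseline scores in the arm comparisons, although the same instruments are given at baseline, 3 and 6 months. With 35 per arm, adjustment would narrow the 95% interval by 4% to 28% for r from 0.3 to 0.7, and would widen it by about 1% if r were 0. These figures assume a linear relation with a common SD and slope in both arms, full follow-up (28 per arm gives nearly the same percentages), and an r that the documents do not supply and that may be near the low end.

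It would be wrong to conclude that the planned estimates are biased, that the feasibility and acceptability aims are weakened, or that the definitive trial's sample size is affected. Randomisation protects the simple difference, the Data Analysis Plan makes feasibility and acceptability primary, and it ties the definitive trial to retention and viral load. AUDIT-C and ASSIST are outside the point, because the Sample Size section does not name substance use among the exploratory arm comparisons.

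**What to change.** Optional, exploratory outcomes only. Add to the Data Analysis Plan that, for each coping subscale (avoidance, positive, seeking social support), the IARSS and each DASS-21 subscale, the arm difference at 3 months and at 6 months will be estimated by a separate ANCOVA with arm and the baseline value of the same score, and reported with a 95% confidence interval. Add the condition that the baseline score was recorded before the arm was disclosed; otherwise the unadjusted difference is reported. The condition is needed because the trial is unblinded, and a self-report given after the arm is known may already reflect it.

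The cost is a sentence or two of text and one degree of freedom per model (about 1% in interval width at r = 0), with no new data. That cost holds only if the baseline survey already precedes disclosure. If it does not, either the visit procedure must change or the unadjusted difference should be kept.

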- Never in care or currently out of HIV care for HIV, defined as not meeting the 'visit constancy' measure (completed HIV primary care visit in a Houston area clinic in each of the three 4-month intervals preceding admission); or 2 or more "no shows" to HIV primary care visits in a Houston area clinic in the last year. All persons with VL>1000 c/mL would be expected to be seen 3 times in a given year, and "no shows" to clinic visits have been independently predictive of increased morbidity and mortality, especially in Black PWH.
- Endorse one of the two avoidance coping statements with the highest factor loadings on the Avoidant Coping Subscale from the Coping with HIV/AIDS scale.

Exclusion Criteria

All candidates meeting any of the exclusion criteria will be excluded from study participation.

Exclusion criteria are:

- Intending to use a source of HIV primary care other than Thomas Street Health Center (TSHC) after discharge, because their outcomes cannot be evaluated (>70% of PWH hospitalized at BTH intend to use TSHC after discharge)
- In the opinion of the primary medical team caring for the patient, likely to be discharged to an institutional setting, die in the hospital or enter hospice
- Incarcerated or expected to be discharged to prison or jail
- Enrolled in another research study with prospective follow-up
- Pregnant, since pregnant women receive additional efforts to be linked and retained in care
- Admitted with acute psychosis which would preclude informed consent or meaningful participation with the intervention.

Sample Size

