The Harris Health EMR, an Epic product, is accessible via Citrix on any computer. Researchers can review the entire EMR from their research offices, including discharge summaries, inpatient and outpatient notes, laboratory results, all appointment schedules, and prescriptions. Epic data include appointment, laboratory, and ART data on all patients seen at BTH, TSHC or one of its satellite HIV clinics from 2002 to present. Appointment data include all visits at TSHC, including HIV primary care, mental health, and chemical dependency counselor visits. Clinic visit data include whether the visit was kept, missed, cancelled, or rescheduled. Dates of hospitalization at BTH are included. Completed and missed visit data will be abstracted from Epic. The Centralized Patient Care Data Management System (CPCDMS) is a regional database in which clients must be registered to receive medical and case management services funded by the 6-county Ryan White Part A funds. CPCDMS will indicate if participants have transferred care from TSHC to other Ryan White-funded providers, substantially reducing the chance of misclassifying patients regarding care re-engagement.

[6-month Viral Load](#)

All patients have a VL done as standard of care in the hospital. We will obtain 6-month VL by study phlebotomy in the field (not at the clinic, to avoid biasing participants) if none are available in the EMR, and review the EMR for additional VLs to minimize missing data. All VL assays will be conducted by the BTH laboratory, a fully certified clinical laboratory that performs all HIV-related laboratory studies for TSHC and BTH.

Data Collection and Quality Assurance

REDCap

All data collection forms will be available through a REDCap (Research Electronic Data Capture) database and patients can directly enter data into these forms. They will enter data into a central database through a study computer. This will eliminate error in data entry, and reduce time necessary for data entry, cleaning and analysis. Range checks will be programmed into the data entry system when the nature of the data allows so that it will not permit invalid values to be entered into the database.

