The Client Satisfaction Questionnaire (CSQ) (Larsen et al., 1979), is an 8-item, empirically derived, self-report measure is widely used to assess patient satisfaction with services. The instrument was designed to assess satisfaction with a specific service, rather than health care in general (Atkisson et al., 1999) and thus is appropriate for measuring participants' satisfaction with THRIVE. The CSQ's psychometric properties are strong, and it has been widely used in adults and adolescents with HIV, including persons with substance use and mental health problems (Fals-Stewart, 2010; Hosek, 2011). In addition, we will include a single-item measure of overall satisfaction with the intervention and a single-item measure of likelihood of recommending the intervention to others.

Chart Review

The Harris Health EMR, an Epic product, is accessible via Citrix on any computer. Researchers can review the entire EMR from their research offices, including discharge summaries, inpatient and outpatient notes, laboratory results, all appointment schedules, and prescriptions. Epic data include appointment,

laboratory, and ART data on all patients seen at BTH, TSHC or one of its satellite HIV clinics from 2002 to present. Appointment data include all visits at TSHC, including HIV primary care, mental health, and chemical dependency counselor visits. Clinic visit data include whether the visit was kept, missed, cancelled, or rescheduled. Dates of hospitalization at BTH are included. Completed and missed visit data will be abstracted from Epic. The Centralized Patient Care Data Management System (CPCDMS) is a regional database in which clients must be registered in order to receive medical and case management services funded by the 6-county Ryan White Part A funds. CPCDMS will indicate if participants have transferred care from TSHC to other Ryan White-funded providers, substantially reducing the chance of misclassifying patients regarding care re-engagement.

[Blood Draw](#)

All patients have a VL done as standard of care in the hospital. Then at 6-month, a VL by study phlebotomy in the field (not at the clinic, to avoid biasing participants) will be conducted if there is not one in the EMR, and a review the EMR for additional VLs to minimize missing data. All VL assays will be conducted by the BTH laboratory, a fully certified clinical laboratory that performs all HIV-related laboratory studies for TSHC and BTH.

[Data Analysis Plan](#)

[Analysis Methods](#)

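### The plan gives two different rules for obtaining the 6-month viral load, and sets neither a date window for record values nor a rule for which of several values is scored

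*Combined protocol and SAP*

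**What the plan says.** Three sections of the combined protocol and SAP describe how the 6-month VL is obtained.

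- **Evaluation Overview** (Post-Intervention Evaluations) sets no condition: "We will obtain 6-month VL by study phlebotomy in the field (not at the clinic, to avoid biasing participants to return to the clinic". EMR values are reviewed as additional ones. It adds: "About 10 mL of blood will be drawn per participant at the 6-month evaluation".
- **6-month Viral Load** has the sample taken "by study phlebotomy in the field (not at the clinic, to avoid biasing participants) if none are available in the EMR".
- **Blood Draw** (Data Collection Instruments) says the field draw "will be conducted if there is not one in the EMR".

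All three also state that every patient has a VL measured during the admission.

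Related text:

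- Sample Size describes the arm comparison as on "retention in care and undetectable VL 6 months after hospital discharge", with no window. The Summary of Measures table lists HIV VL as a primary outcome.
- The Evaluation Overview extends the record review to a year past enrolment, bars follow-up assessments from the HIV clinic, and adds: "Phone interviews will be used for follow-up assessments as a last resort".
- Analysis Methods sets a feasibility benchmark: at least 80% of participants alive at 6 months must have appointment data and a 6-month VL. It does not define a 6-month VL.

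**The concern.** The sections differ on whether a participant with a recent clinic VL is drawn, and the conditional version cannot be applied as written without a date limit.

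The difference bears on a primary outcome. The Evaluation Overview takes care to separate measurement from clinic attendance: assessments happen away from the HIV clinic, and the draw is in the field so that payment does not pull people back to it. An EMR-first rule with no window partly undoes this. Someone who returns to care generates routine VLs on dates set by care. Someone who does not return is measured at the study visit. Attendance is what the intervention is meant to change, so the date and source of the VL could differ by arm.

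Study personnel are also unblinded (Blinding section). Where several values exist and no rule picks among them, the choice can be made with the arm known.

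Two products of the pilot are exposed: the arm estimates meant to support the definitive trial, and the feasibility count for 6-month VL data.

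**Working it through.** **1. The plan's own precision figure, as a yardstick.** Sample Size gives 35 per group, a composite rate of 30% to 65%, and a 95% CI of 15 to 17 points either side. The Wald half-width is 1.96 × √(p(1−p)/35):

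- p = 0.30: 15.2 points
- p = 0.50: 16.6 points
- p = 0.65: 15.8 points

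The stated figure is reproduced and is not in question.

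**2. The sections applied to the same participant.**

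| Post-discharge VLs in the EMR at the 6-month visit | Evaluation Overview | 6-month Viral Load; Blood Draw |
|---|---|---|
| None | Draw | Draw |
| One, dated at month 6 | Draw; EMR value is additional | Draw not called for |
| One, dated for example at month 4 | Draw; EMR value is additional | Undetermined: no window |

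The sections agree only in the first row.

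**3. The EMR condition read literally.** Every patient has an in-hospital VL. If any VL in the EMR counted, the condition for a field draw would never be met. The sensible reading is that a 6-month VL is meant, as the heading and the sentence suggest. That reading needs a width around month 6, and none is stated.

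**4. Several values.** The 6-month Viral Load section also looks for additional EMR values, and the record review runs to a year past enrolment. A participant can therefore have values before and after month 6, with or without a study draw. No section says whether the study draw, the nearest value or the last value is scored.

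**5. Scale.** If k of the 35 participants in an arm are scored differently because of the value chosen, and all in the same direction, that arm's rate moves by k/35:

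- k = 1: 2.9 points
- k = 3: 8.6 points
- k = 6: 17.1 points, about the full stated half-width

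The documents give no basis for any particular k. These are assumed values, not estimates.

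**6. The feasibility benchmark.** If all 70 are alive at 6 months, 0.80 × 70 = 56 must have the data and 70 − 56 = 14 may lack it. Under either wording, a participant seen in person with no qualifying EMR value is due a draw. If the draw decision and the benchmark use the same window, the window changes the count mainly for people who are not drawn: those followed only by phone, unreachable or refusing. For them an EMR value may be the only one. Their number is not given.

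**7. Does the payment schedule settle it?** 20 + 30 + 40 + 20 + 5 + 5 + 5 = $125, of which $20 is for the 6-month draw. The total is stated as a maximum, so it fits either rule.

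**The case against.** The best defence is that the Evaluation Overview is only an overview. The two dedicated sections agree with each other, and reading them as refinements gives a workable EMR-first rule. The per-participant sentence may merely state a blood volume. The 6-month list, "At 6 months, the survey will include: Coping; IARSS; DASS-21; AUDIT-C; ASSIST; Chart Review; and HIV VL", names VL apart from chart review, but it is plainly shorthand, since neither is a survey item. These points have force. They soften the conflict but do not remove it, because the plan does not say which section governs. The missing window and selection rule remain on any reading.

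A reader might infer that staff cannot comply with all three sections. That goes too far: drawing everyone satisfies the overview, and the other two sections do not forbid it.

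A reader might also try to work out how many draws an EMR value would replace, starting from "All persons with VL>1000 c/mL would be expected to be seen 3 times in a given year". The documents do not support this. That sentence explains an eligibility criterion and is not a VL testing schedule. The criteria largely select people who have not kept to that pattern. Visits and month 6 are both tied to discharge, so their timing may be linked. A count of earlier values also ignores those dated after month 6.

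Finally, this is a pilot with no efficacy tests, and feasibility and acceptability are its primary aims. That limits the consequence. It does not excuse the gap, because the estimates and feasibility counts are meant to inform the definitive trial.

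**Conclusion.** The point holds and should be fixed. The sections conflict on how a listed primary outcome is obtained, and the date limit that the EMR-first rule needs is missing, as is any rule for choosing among values. Confidence is high on those textual findings.

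Under the EMR-first rule, the timing of the VL can depend on attendance. This assumes only that routine VLs arise from clinic visits. A reader might infer that the arm difference is biased, or biased in favour of THRIVE. The documents do not show this: neither size nor direction can be determined from them, and the 2.9 points per participant is a scale, not an estimate.

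Nor do the documents show that the 80% benchmark as a whole is in doubt. Its dependence on the window is mainly confined to participants who are not drawn.

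**What to change.** Reconcile Evaluation Overview, 6-month Viral Load and Blood Draw to one rule, applied identically in both arms and stated before analysis.

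- **Preferred:** keep the field draw for all, within a prespecified window around 6 months after discharge. Use the in-window EMR VL closest to month 6 only when the draw is missed. The width is for the sponsor to set; ±30 days is only an example and does not come from the documents.
- **If EMR-first is kept:** accept an EMR VL only inside that window, take the one closest to month 6, and otherwise do the field draw.
- **Either way:** use the same window for the feasibility benchmark, including for participants followed by phone, and record the source and date of each VL scored.

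**Cost:** protocol wording and two data fields. The preferred rule means more field draws than the two conditional sections imply, though the Evaluation Overview already plans them. Draw payments are at most 70 × $20 = $1,400, already inside the $125 per-participant maximum. Staff and assay costs are not in the documents. Excluding out-of-window EMR results may add a few missing values, which works against the purpose of the EMR review. The preferred rule also leaves some dependence on attendance among those who miss the draw, but confines it to the window.
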